4.3 Subject Recruitment

Potential subjects will be informed of this study by:

- Verbal communication from licensed site investigators during routine patient clinical visits.
 Licensed site investigators may also provide a printed flier about the study to their patients
- Email or phone call, if permitted, to individuals who have consented, in the past as part of a separate research study, to being re-contacted for participation in future research studies
- Email or phone call, to individuals who have been identified via Epic Best Practice Advisories and Slicer Dicer, who have consented to be contacted for participation in research studies
- The Castleman Disease Collaborative Network (CDCN), a nonprofit organization dedicated to supporting Castleman disease patients and accelerating research.
 - The CDCN has a network of physicians located throughout the United States.
 These physicians have expressed interest in providing information to their patients
 about research studies. If a physician in the CDCN chooses to approach their
 patient with information regarding this study, they will provide the individual with a
 flier
- ClinicalTrials.gov, which will list this study along with contact information for the Site Principal Investigators and study coordinators

Subject recruitment will not use any University of Pennsylvania media services. Any interested subject will be referred to a licensed site investigator for eligibility determination.

4.4 Duration of Study Participation

The Screening/Baseline Phase will include an on-site visit and may last 0 - 28 days. The Intervention Phase will last up to 12 ± 1 month, and the Follow Up Phase will be approximately 12 ± 2 weeks. In total, each subject's participation will last up to 73 weeks.

4.5 Total Number of Subjects and Sites

Up to 40 subjects may enroll into this study to achieve the intended goal of up to 24 evaluable subjects. To determine if the trial will continue, an interim analysis will be completed after 14 subjects have completed the Visit 9 intermediate assessment. This trial involves up to four sites, which are expected to have approximately equal enrollment rates.

4.6 Vulnerable Populations:

Children 2 years of age or older may be considered for this study. Pregnant women, fetuses, neonates, and prisoners are not included in this research study.

5 Study Intervention

5.1 Description

SIROLIMUS (AY-22989, rapamycin, Rapamune®) NSC# 226080 (092405). Sirolimus is available as a tan, triangular-shaped tablet containing 0.5 mg sirolimus; a white, triangular-shaped tablet containing 1 mg sirolimus; and a yellow to beige triangular-shaped tablet containing 2 mg sirolimus. The inactive ingredients in sirolimus tablets include sucrose, lactose, polyethylene glycol 8000, calcium sulfate, microcrystalline cellulose, pharmaceutical glaze, talc, titanium dioxide, magnesium stearate, povidone, poloxamer 188, polyethylene glycol 20,000, glyceryl

monooleate, carnauba wax, and other ingredients. The 2 mg dosage strength also contains iron oxide yellow 10 and iron oxide brown 70. Sirolimus is commercially available. The prescribing information for Rapamune can be found at:

https://www.accessdata.fda.gov/drugsatfda_docs/label/2018/021083s061,021110s080lbl.pdf.

5.2 Intervention Regimen

Adult subjects will receive sirolimus orally, a loading dose of 5 mg/m², rounded to the nearest mg, on day 1. Loading dose may be lower at the discretion of the prescribing physician. Starting on day 2, adult subjects will take oral sirolimus daily at 2.5 mg/m²/day (rounded to the nearest mg), target trough level 10-15 ng/mL, based on tolerability. Pediatric subjects will not receive a loading dose, and daily dosing will be at 2 mg/m²/day (rounded to the nearest mg), adjusted to achieve a target trough level of 5-15 ng/mL. Sirolimus trough levels will be determined at approximately Day 5, Day 14, Months 1, 3, 6, 9, and 12 (see **Appendix 15.3** for the study calendar). At the discretion of the study doctor, additional sirolimus trough levels may be obtained. Sirolimus trough levels will be determined in a clinical grade laboratory, which may be located at the study center or at a clinical facility close to the subject, if more convenient.

Frequent dose adjustments based on non-steady-state sirolimus concentrations can lead to overdosing or under dosing because sirolimus has a long half-life. Once maintenance dose is adjusted, patients should continue on the new maintenance dose for at least 7 to 14 days before further dosage adjustment with concentration monitoring. In most patients, dose adjustments can be based on simple proportion: new dose = current dose × (target concentration/current concentration). Dose adjustments are based on clinical judgment of the licensed site investigator after considering clinical toxicity, serum levels, concomitant drug use and the rate of rise or decline of the serum level. For levels < 10 ng/mL, it is suggested, but not required, that the dose of sirolimus be increased, but not to exceed a maximum daily dose of 40 mg. Conversely, for levels > 15 ng/mL, it is suggested, but not required, that the dose be decreased. Alternatively, sirolimus can be withheld entirely as long as serum levels are monitored and the drug is restarted when the level returns to the therapeutic range and the licensed site investigator feels it is appropriate to restart the agent. It is suggested, but not required, that levels of sirolimus be drawn at least weekly until steady state, then monitored thereafter unless a change in medication (e.g. use of voriconazole) or renal function might result in an acute change in level. At that point, levels should be measured as clinically indicated. The anticipated length of treatment will be 12 months. iMCD is a chronic condition and, as sirolimus is commercially available for other indications, patients who show improvement on sirolimus may remain on treatment indefinitely at the discretion of their physician. Examples of dose calculations are provided in Appendix 15.5 Example Dose Calculations.

5.3 Receipt

All drug will be obtained from a commercial producer (Pfizer) and be received by the investigational pharmacy at each participating site. Upon receipt of the study treatment supplies, an inventory will be performed and a drug receipt log filled out and signed by the person accepting the shipment. The designated study staff will count and verify that the shipment contains all the items noted in the shipment inventory. Any damaged or unusable study drug in a given shipment will be documented in the study files. The IDS and the IP will notify the Lead Principal Investigator of any damaged or unusable study treatments that were supplied. All drug will be supplied in bulk.

5.4 Storage

Sirolimus tablets should be stored at controlled room temperature, which is 20-25 °C with excursions permitted between 15 °C - 30 °C. The investigational pharmacist at the IDS and the IP will ensure that all study drug is stored in a secured area, under recommended storage conditions, including with regards to protection from light and sterile conditions, and in accordance with applicable regulatory requirements, and will be dispensed by qualified staff members. The pharmacist will maintain accurate records regarding study drug administration and return.

5.5 Preparation and Packaging

Sirolimus tablets will be prepared by a commercial producer (Pfizer) and will be packaged by the investigational pharmacist at the IDS and the IP in child-resistant bottles for dispensation to subjects. Bottles will be labeled to meet state and FDA requirements.

5.6 Administration and Accountability

The IDS and IP service will maintain accurate logs of study drug dispensing, and will conduct regular drug reconciliation checks to document drug assigned, drug consumed, drug remaining, product damage/destroyed and return of damaged/destroyed drug, along with dates of such damage and return. This reconciliation will be logged on the drug reconciliation form, and signed and dated by the service.

Sirolimus will be provided to patients at on-site visits or shipped to subjects as needed (e.g. if their supply is lost, or if results from remote sirolimus trough assays results in a dose adjustment). Sirolimus will be administered orally and should be taken at a consistent time of day and at consistent intervals with regard to meals. Sirolimus may be given with food as long as it is given the same way each time; however, administration with food significantly alters the rate and extent of absorption.

5.7 Subject Compliance Monitoring

At each on-site visit, compliance with study drug will be reinforced; study drug bottles will be returned and compliance will be assessed by pill count. Subjects will be provided a medication diary to complete at home, which will be reviewed at each on-site visit. Study medication dispensed or returned to IDS or the IP must be recorded for Drug Accountability and Reconciliation at each on-site visit in a standard form. Serum trough levels of sirolimus will be monitored. Patients will be informed to withhold their daily dose of sirolimus until after a clinical blood sample is drawn to assay for trough levels of sirolimus.

Non-compliance is defined as two consecutive study visits with >30% of study drug not consumed. Non-compliant patients will receive counseling from the licensed site investigator and be warned that they may be removed from the study. If there is a third study visit with >30% of study drug not consumed, then the licensed site investigator will determine if the subject should be removed from the study.

5.8 Return or Destruction of Investigational Product

At the completion of the study – following the last enrolled patient's final assessment - there will be a final reconciliation of drug shipped, drug consumed, and drug remaining by IDS and the IP. This reconciliation will be logged on the drug reconciliation form, signed and dated. Any discrepancies noted will be investigated, resolved, and documented prior to return or destruction of unused study drug. Drug destroyed on site will be documented in the study files.

6 Study Procedures

Radiological Imaging

Computed tomography (CT) with contrast or positron emission tomography/CT (PET/CT) scan images conducted as standard of care treatment for iMCD will be centrally reviewed by a radiologist at the University of Pennsylvania. PET/CT will be full body imaging, and CT will include neck, chest, abdomen and pelvis. The site physician should maintain consistency, as is medically appropriate, in imaging modality utilized for each subject to that used at the Baseline Visit.

Blood Draws

No more than 100 mL of blood will be drawn at the Baseline Visit, and no more than 55 mL at each subsequent Visit specifically for research laboratory (i.e. non-clinical health or sirolimus monitoring) purposes. Blood will be drawn into ethylenediaminetetraacetic acid (EDTA) coated tubes (Baseline Visit: 80 mL; subsequent Visits: 40 mL) and serum separator tubes (Baseline Visit: 14 mL; subsequent Visits: 7 mL).

Research samples obtained during on-site visits will be processed at the site or shipped to the University of Pennsylvania for processing. Those obtained during remote visits will be shipped to the University of Pennsylvania for processing. Subjects will be provided with appropriate shipping materials and instructions regarding how to ship research samples to the University of Pennsylvania.

Fecal Sample Collections

Fecal samples will be collected at the Baseline Visit, prior to starting sirolimus, at Week 2, and at Visit 9. Fecal sample collections are optional.

Fluid Sample Collections

Fluid samples, such as those collected during paracentesis, may be collected and stored for research analysis. Samples will be shipped to the University of Pennsylvania or the Children's Hospital of Philadelphia for processing, or may be processed at the site.

Clinical Laboratory Testing

For standard of care laboratory testing conducted by a third-party provider, the site physician should maintain consistency in the provider used for the Baseline Visit testing for each subject, as is medically appropriate.

Please see **Appendix 15.3** for the study calendar.

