4.1 Inclusion Criteria

To be eligible, subjects must meet all of the below inclusion criteria:

- 1. Male or female, age 2-80
- Documented disease history consistent with the diagnostic criteria for iMCD (Appendix 15.1)
 - Confirmation of clinico-histopathological features by licensed pathologist, or a CAS grade of at least 3 in the companion registry study (ACCELERATE)
- 3. Failed/refractory (patient did not achieve sufficient disease control with anti-IL-6 therapy, as determined by the site investigator), relapsed (return of symptoms while on therapy), or inability to tolerate anti-IL-6 or anti-IL-6 receptor therapy
- 4. Evidence of active disease, defined as at least two abnormalities in the criteria comprising the CBR criteria and as defined as abnormal by CTCAE v4.0, including at least one objective measurement (hemoglobin, weight loss, or lymph node size)
 - Hemoglobin < lower limit of normal
 - Fatigue, including fatigue relieved by rest
 - Anorexia, including loss of appetite without alteration in eating habits
 - Fever or night sweats
 - Weight loss ≥ 5% from baseline
 - At least one lymph node meeting modified Cheson criteria (**Appendix 15.2**)
- 5. Ability to consume oral medication in the form of a tablet
- 6. Ability to provide, or for a LAR to provide on their behalf, informed consent prior to any study-specific activities

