7.6 Efficacy Evaluations

The below measures will be used to assess the efficacy of the study intervention and determine if the subject meets criteria for a CBR. All comparisons are against those obtained during the Baseline Visit:

Positive response: Relative to baseline, improvement in at least one of the below criterion without worsening of any single criterion other than hemoglobin on two consecutive study visits.

Negative response: Relative to baseline, worsening of any single criterion other than hemoglobin on two consecutive site visits or failure to achieve improvement for any criterion.

	Hemoglobin	Fatigue	Anorexia	Fever and night sweats	Weight	Lymph node size
Improvement	≥2 g/dL increase without transfusions	≥1 grade decrease by NCI CTCAE version 4.0, May, 2009	≥1 grade decrease by NCI CTCAE version 4.0, May, 2009	≥2°C decrease in fever or return to normal body temperature (37°C) or improvement in night sweats, as assessed by licensed site investigator	≥5% increase not due to increase in new or existing edema	≥25% decrease bi-dimensionally in size of largest lymph node, as measured using Cheson criteria (Appendix 15.2)
Worsening		≥2 grade increase by NCI CTCAE version 4.0, May, 2009	≥2 grade increase by NCI CTCAE version 4.0, May, 2009	≥2°C increase in fever or worsening in night sweats, as assessed by licensed site investigator	≥5% decrease (weight loss not due to decreased edema)	≥25% increase bidimensionally in size of largest lymph node, as measured using Cheson criteria (Appendix 15.2)

The below table provides the CHAP score, which will be used to assess the efficacy of the study intervention. All comparisons are against those obtained during the Baseline Visit:

Score:	0	1	2	3	4
CRP (mg/dL)	<1	≥1, <5	≥5, <10	≥10, <20	≥20
Hemoglobin (g/dL)	≥12	<12, ≥10	<10,≥8	<8	Transfusion dependent
Albumin (g/dL)	≥3	<3,≥2.5	<2.5, ≥2	<2, ≥1.5	<1.5
Performance Score (ECOG)	0	1	2	3	4

The below table provides the modified Cheson response criteria, which will be used to assess the efficacy of the study intervention. Unless otherwise specified, all comparisons are against those obtained during the Baseline Visit:

Complete Response (CR)	All index lesion(s) must have regressed to normal size (≤1.0 cm in		
	their greatest transverse diameter. No new sites of		
	lymphadenopathy >1.5 cm in longest dimension.		
Partial Response (PR)	≥50% decrease in sum of the products of the greatest diameters		

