15.3 Study calendar

Study Phase	Screening	Baseline Phase	Intervention Phase							Early	Follow-up Phase							
Study Visit Number	Screening	1	2	3	4	5	6	7	8	9	10	11	12	13	14	15	Terminati	16
Study Days**	-28 to 0**	-7 to 0**	5 ± 2 days	14 ± 5 days	1 month ± 1 week	2 months ± 2 weeks	3 months ± 2 weeks	4 months ± 2 weeks	5 months ± 2 weeks	6 months ± 2 weeks	7 months ± 2 weeks	8 months ± 2 weeks		10 months ± 2 weeks			on Visit	12 ± 2 weeks following the End of Study Visit
Diagnostic Laboratory Tests*	Х																	
Physical Exam*		X			X***		X***			X***			X***			X***	X***	
Vital Signs*	x	x			X***		X***			X***			X***			X***	X***	
Radiological Imaging*	X						X			X			X			x		
Lipid Panel	x	X			X		X			x			X			x		
Review of concomitant medications*	X	X																
Confirmation subject meets enrollment criteria	x	x																
Informed Consent	x																	
Pregnancy Test (urine)	X				X		X			X			X			x	X	
GUID assigned		X																
Research blood draw		X	x	х	X	х	X	X	X	X	x	X	X	x	х	х	X	
Fecal sample collection (optional)		X		X						X								
Recording of Demographic information in to eCRF	x																	
Recording of medical history data, medications, possible AEs and Laboratory Test, as available, from medical records into eCRF		x	x	x	х	x	x	x	x	x	x	x	x	x	x	x	x	
Completion of Patient Evaluation Form and confirmation subject is eligible by Lead PI	x	x																
Dispensing of sirolimus loading dose**		x																
Dispensing of sirolimus daily dose		X			X		X			X			X					
Assess possible AEs, study drug compliance, and medication changes			x	x	x	x	x	x	x	x	x	x	x	x	x	x	x	х
Sirolimus Trough			x	X	X		X			X			X			х	x	
Standard of Care Laboratory Test*					X		X			X			X			X	X	
Return of any non-consumed sirolimus					X		X			x			X			x	x	
Sirolimus pill count***					X		X			X			X			X	X	
Intermediate assessment of primary objective							x			x				x		^	~	
Final assessment of primary objective																x		
Follow Up telephone questionnaire																		X

^{*}Standard of Care for iMCD

^{**}Indicated times are following loading dose

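### Section 6 sets the same research blood volumes for every subject, with no pediatric limit, although children from age 2 and markedly anemic subjects are eligible

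*Combined protocol and SAP*

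**What the plan says.** Section 6 (Study Procedures, Blood Draws) caps research blood per visit: "No more than 100 mL of blood will be drawn at the Baseline Visit, and no more than 55 mL at each subsequent Visit". The cap covers blood taken "specifically for research laboratory (i.e. non-clinical health or sirolimus monitoring) purposes", so clinical laboratory tests and sirolimus troughs come on top. The section then lists the planned tubes. EDTA tubes are given as "Baseline Visit: 80 mL; subsequent Visits: 40 mL", and serum separator tubes add 14 mL at baseline and 7 mL at later visits.

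The entry "Research blood draw" is marked in the study calendar (Appendix 15.3) at each of Visits 1 to 15, and Sections 6.2.1 to 6.2.11 list it visit by visit. Section 6.2.1 applies the baseline research procedures to all subjects. Fecal sampling is labelled optional; research blood is not.

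The first inclusion criterion in Section 4.1 reads "Male or female, age 2-80", and Section 4.6 confirms: "Children 2 years of age or older may be considered for this study". Section 4.2 excludes hemoglobin only at 6.5 g/dL or below. The protocol has separate pediatric rules for sirolimus dose and trough target (Sections 1.3, 3.1 and 5.2) and for neutrophil count and performance score (Section 4.2). It has none for blood volume.

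**The concern.** One set of volumes covers an age range from toddlers to 80-year-olds. An amount that is small for an adult is a large share of a small child's circulating blood, and four of the fifteen draws fall within about the first month. The subjects may already be anemic, since low hemoglobin is one way to show active disease at entry, and the blood is taken for research, not for care. Section 6.2.2 allows Visits 2 and 3 to take place at a local commercial laboratory. Nothing in the protocol text would tell staff there to draw less from a child. What is at stake is the safety of the smallest subjects.

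**Working it through.** **Inputs from the protocol (Section 6 and Appendix 15.3)**
- Tubes at baseline: 80 + 14 = 94 mL, within the 100 mL ceiling.
- Tubes at each later visit: 40 + 7 = 47 mL, within the 55 mL ceiling.
- Research draws up to about one month: Visit 1 (baseline), Visit 2 (day 5), Visit 3 (day 14) and Visit 4 (1 month).
- Research draws in all: Visit 1 plus 14 later visits.

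The tubes and ceilings agree with each other. The protocol states no cumulative or per-kg figure, so there is none to reproduce.

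**Assumptions, not in the protocol**
- Blood volume of 70-80 mL per kg.
- Body weights of 12 kg (roughly the youngest eligible child), 18 kg and 25 kg.

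**Cumulative volume**
- By Visit 4, stated tubes: 94 + 3 x 47 = 235 mL.
- By Visit 4, at the ceilings: 100 + 3 x 55 = 265 mL.
- Visits 1 to 15, stated tubes: 94 + 14 x 47 = 752 mL.

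**Share of blood volume** = volume drawn / (weight x mL per kg), gross, before regeneration

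| Weight | Blood volume | Baseline, 94 mL | By Visit 4, 235 mL |
|---|---|---|---|
| 12 kg | 840-960 mL | 9.8-11.2% | 24.5-28.0% |
| 18 kg | 1260-1440 mL | 6.5-7.5% | 16.3-18.7% |
| 25 kg | 1750-2000 mL | 4.7-5.4% | 11.8-13.4% |
| 70 kg adult | 4900-5600 mL | 1.7-1.9% | 4.2-4.8% |

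At the ceilings, the 12 kg figure by Visit 4 is 265/960 to 265/840 = 27.6-31.5%.

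**Possible size of a hemoglobin effect**, taking 10 g/dL and 12 kg as a further illustration
- First month, no regeneration, simple proportion: 10 x 0.245 to 10 x 0.280, a fall of about 2.5-2.8 g/dL. If volume is replaced continuously, 10 x (1 - exp(-f)), with f the share removed, gives about 2.2-2.4 g/dL. Both are upper bounds. The first scheduled CBR assessment is not until month 3.
- Around month 12, draws are about monthly. One draw is 47/960 to 47/840 = 4.9-5.6% of blood volume. If only one earlier draw were unrecovered, the fall would be about 0.5-0.6 g/dL, against the 2 g/dL improvement threshold. Slower recovery would give more.

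**The case against.** Several points on the other side have force. The headline share is gross cumulative volume over four draws, not a net deficit, and about a quarter applies only near 12-14 kg. Weight and mL per kg are outside assumptions. The Section 6 sentence is a ceiling, so a site may draw less. The inclusion criterion on swallowing tablets may keep out some of the smallest children, and the protocol gives no expected number of children. A limit may exist in consent pages not available for this review or in local IRB rules; Section 10.4 says that the children's hospital uses its own IRB. These points limit how many children are exposed and how far. None of them puts a pediatric limit into the protocol, and the tube volumes are stated as what will be collected.

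A reader might also infer that the trial's own sampling biases its primary endpoint, because hemoglobin is one of the six CBR criteria. The documents do not support that. Section 7.6 excludes hemoglobin from CBR worsening, so blood loss cannot by itself turn a response negative through that route. It could at most hide an improvement, defined as at least a "2 g/dL increase without transfusions", or raise the hemoglobin component of CHAP. Improvement in any one of the six criteria is enough for a positive CBR. The primary assessment is at 12 ± 1 months (Sections 3.2.1 and 8.1), long after the closely spaced draws. Any such bias would run against sirolimus, not toward false efficacy.

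**Conclusion.** The gap is real and should be closed before a small child is sampled. Followed as written, Section 6 takes about 10-11% of a 12 kg child's blood volume at baseline and a cumulative gross 24-28% by about one month, for research only. The figures fall to 16-19% at 18 kg and 12-13% at 25 kg. The volumes are the protocol's own; the percentages rest on the assumed weights and 70-80 mL per kg, and ignore regeneration.

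The case rests on pediatric safety alone. The endpoint consequence is only a caveat: a masked hemoglobin gain or a higher CHAP score in a few small children, mainly at early visits. No material effect on the 12-month CBR is shown.

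**What to change.** In Section 6, Blood Draws:
- Restrict the 94 mL and 47 mL tube volumes, and the matching ceilings, to adults.
- For pediatric subjects, add a research-blood ceiling by body weight, per draw and per period. The pediatric investigators and their IRB should set the value; none is proposed here.
- State the order in which research tubes are dropped when the ceiling is reached.

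If a limit already exists in consent or IRB documents, restating it in Section 6 is enough for the ceiling. The cost is a short edit and less research sample from a few children. The primary endpoint, the visit schedule and the analysis do not change.
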